# STUDY PROTOCOL

## Research Abstract

Over 100 million Americans suffer from high blood pressure and thus are at increased risk for cardiovascular disease and premature morality. Evidence supports the DASH (Dietary Approaches to Stop Hypertension) dietary pattern to reduce blood pressure. DASH is rich in fruits and vegetables, legumes, lean protein, and low-fat dairy, and reduced in red meats, sweets and processed foods. In the past 20 years, numerous trials have demonstrated the blood pressure-lowering effects of DASH across a diverse range of populations. As such, DASH is part of national dietary and blood pressure guidelines. Despite this strong evidence, fewer than 1% of U.S. adults with high blood pressure fully meet DASH guidelines. Like most efficacious interventions, the rate-limiting step involves dissemination. Behavioral trials testing DASH have been delivered primarily in-person, an approach that is effective but not accessible to the broader population. Innovative and accessible strategies to disseminate DASH, such as digital health, are critically needed. To address this need, we developed and tested the feasibility of a 3-month digital health intervention called DASH Cloud. The DASH Cloud intervention asked participants to track their diet daily using a commonly-used commercial tracking app with an extensive nutrient database. Our intervention technology platform extracted food and nutrient data from the app using an application programming interface (API). Each day, using this API software, we compared individual participant's nutrient intake to the recommended levels in the DASH diet. We then processed the data against an algorithm and sent automated text messages to each participant with information on DASH diet adherence and diet tips. Results indicated that we successfully recruited and retained individuals with elevated blood pressure, achieved high engagement with daily diet tracking and saw positive changes in diet quality. Based on the results of the feasibility trial, we will improve upon the personalization of the automated text messages and include a scalable and responsive way of delivering coaching, based on diet data received in the app. The efficacy of this approach will be tested via a fully-powered 12-month randomized controlled trial, Nourish. The trial will examine the effects of the intervention on changes in dietary quality and blood pressure among men and women with high blood pressure, using the new blood pressure guidelines for nonpharmacological treatment. The primary outcome is 6-month change in DASH adherence, as measured by 24-hour recalls. We will also measure DASH adherence at 12-months post-randomization. Secondary outcomes include changes in blood pressure and other physiological outcomes (e.g. weight, lipids, glucose). The scientific premise of this proposal represents establishing the efficacy of a previously deemed feasible approach for disseminating the DASH diet. With the millions of Americans in dire need of nonpharmacological treatments for blood pressure, the public health impact of disseminating the Nourish intervention could drastically reduce the incidence of cardiovascular disease. The findings from this study prepare us for a future implementation trial, testing the potential to implement DASH Cloud within clinics and other healthcare institutions, yielding

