## STATISTICAL ANALYSIS PLAN

We hypothesize that the intervention will lead to an increase in average DASH score of 2 units at 6 months and the control arm will achieve a 1-unit increase in DASH score. These estimates are based on the pilot study we conducted where both intervention and control arms achieved a 1-unit increase in DASH adherence from baseline to 3 months. Given the Nourish intervention is more intensive than what was delivered in the pilot, we anticipate a greater increase in DASH adherence. We estimate a standard deviation of 2 units for both intervention and control arms. This results in an effect size of 0.5, which is considered a medium effect size by Cohen's d. With 90% power and a type I error rate (alpha) of .01, a sample size of 242 will allow us to detect a difference of 1 unit in DASH adherence mean change score between study arms. We conservatively assume 20% attrition for this length of follow-up, resulting in the final analytic sample size of 300 total participants. With this sample size, we will also have power to examine intervention effects in systolic and diastolic blood pressure. Using data from the pilot study we anticipate systolic blood pressure changes in intervention vs control as follows: -3.4 (SD=8.6) mmHg and -2 (SD=9.3) mmHg respectively, which results in an effect size of 0.6. The effect size for diastolic blood pressure is 0.75 based on changes in intervention vs control of -3.8 (SD=7.9) mmHg vs. -1.6 (SD=6.4) mmHg, respectively. With 90% power and a type I error rate (alpha) of .01, we can detect the expected effect size with the proposed sample size of 300.

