## Statistical analysis plan

Demographic and baseline data will be examined for integrity of randomization scheme and the homogeneity of study arms. If any demographic and baseline data are not balanced between the two study arms and are believed to affect the outcome, we will consider adjusting these variables in the modeling process. All analyses will be based on intention-to-treat (ITT) principles.

We will assess the overall intervention effect on change of DASH score from baseline to 6 months by a two-sample t-test. To understand how DASH score improves over time from baseline to 6 months, and sustains through 12-month follow-up between study arms, we will plot observed DASH score vs. time (baseline, 2-month, 4- month, 6-month, 12-month) by two study arms. Linear mixed models will be built to test the primary hypotheses. If we observe a linear trend in the previous plot, our model will contain fixed effects including a group variable (intervention vs. control), time, and intervention by time interaction. To account for the correlations within the same participant over time, we will include a random intercept and random slope for time in the model. If there is a quadratic trend in time, we will also include a quadratic term for time in the model. To account for the stratified block randomization design, our models will also include our randomization stratification variables, blood pressure risk category and blood pressure medication status. If any other demographic or baseline variables are statistically different between the two study arms, then these variables will be included in a stepwise model selection process for the linear mixed model. We will evaluate the primary hypotheses by testing the null hypothesis that the time by intervention parameter is 0. Similar analysis will be conducted for changes in blood pressure and relevant clinical, behavioral and psychosocial variables. If the distribution of any of the outcomes is heavily skewed, then we will either appropriately transform the data so it's normally distributed or use a generalized linear mixed model with an appropriate link function.

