Our linear mixed models will be fitted with a full maximum likelihood estimation using all available data to address missing data. These models allow for responses to be missing at random (MAR), where the missing mechanism may be related to either observed covariates or response variables, but not related to the unobserved data. Linear mixed models provide valid estimates of the intervention effect under the MAR mechanism and allow for a broad array of possible reasons for missingness.

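### The test said to decide the primary hypothesis is not a 6-month contrast, and the SAP does not rank it against the 6-month t-test it also plans

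*Combined protocol and SAP*

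**What the plan says.** The Research Abstract defines the endpoint: "The primary outcome is 6-month change in DASH adherence, as measured by 24-hour recalls". Aim 1, under Research Aims for main RCT, is also a 6-month comparison. The opening paragraph of the SAP sizes the trial for the same quantity, assuming gains of 2 and 1 units at 6 months: "a sample size of 242 will allow us to detect a difference of 1 unit in DASH adherence mean change score".

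The analysis subsection of the SAP then gives two analyses:

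- A t-test: "We will assess the overall intervention effect on change of DASH score from baseline to 6 months by a two-sample t-test".
- A mixed model: "Linear mixed models will be built to test the primary hypotheses". The decision rule is "We will evaluate the primary hypotheses by testing the null hypothesis that the time by intervention parameter is 0".

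Time is continuous in the model, with a random intercept and a random slope. Its form is chosen from a plot of observed means by arm at 0, 2, 4, 6 and 12 months: "If we observe a linear trend in the previous plot, our model will contain fixed effects including a group variable", and "If there is a quadratic trend in time, we will also include a quadratic term for time in the model". The missing-data paragraph says the model is fitted "using all available data to address missing data".

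The protocol's Data Analysis & Statistical Considerations section has the mixed model with the same decision rule and no t-test. The section on follow-up visits states that the intervention ends at month 6.

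**The concern.** The endpoint, the aim and the power calculation all concern the between-arm difference in change at month 6. The t-test estimates that difference. The mixed-model parameter is a rate of divergence per month, and no section converts it to a month-6 quantity or limits the model to months 0 to 6.

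Three things are at stake. A real 6-month difference that levels off or wanes during follow-up could be missed. A difference that appears only by month 12 could be read as a 6-month effect. And because neither test is labelled primary and the time form is picked from a plot by arm, the analysis that counts could be settled after the results are visible. The plan extends similar analysis to blood pressure, so the problem carries over to Aim 2.

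**Working it through.** **1. Which test does the 242 belong to?** Inputs from the SAP: difference 1 unit, SD of change 2, alpha .01, power 90%, 1:1 allocation. A two-sided two-sample t-test with 121 per arm (242 in total) has power 0.901, so the stated figure reproduces as the 6-month t-test. After 20% attrition, 300 leaves 240, or 120 per arm. Then SE = 2·√(2/120) = 0.258 and power is 0.903 (normal) or 0.898 (t).

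**2. What the 0–12 month slope estimates.** The documents give no trajectories or variance components, so these are assumed: complete data, 120 per arm, and random-slope variance τ² from 0 to 0.03 per month². Residual variance is s² = (4 − 36τ²)/2, so that the SD of the 6-month change stays at 2.

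Mean visit time is (0+2+4+6+12)/5 = 4.8. The weights t − 4.8 are −4.8, −2.8, −0.8, 1.2 and 7.2, with sum of squares 84.8. Month 12 therefore has six times the weight of month 6. The expected slope is Σ(t − 4.8)·d(t)/84.8, where d(t) is the true arm difference, and SE = √(2(τ² + s²/84.8)/120). This gives 0.0198 at τ² = 0 and 0.0281 at τ² = 0.03.

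Example, linear rise to 1 unit at month 6 and held to month 12: (−2.8/3 − 1.6/3 + 1.2 + 7.2)/84.8 = 6.933/84.8 = 0.0818 per month, and ×6 = 0.49.

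| True arm difference | 6 × slope | Chance slope test rejects at .01 |
|---|---|---|
| Linear to 2 units at month 12 | 1.00 | about 100% |
| Linear to 1 at month 6, held | 0.49 | 63–94% |
| Same, half lost by month 12 | 0.24 | 12–28% |
| Same, all lost by month 12 | about 0 | 1% |
| 1 unit by month 2, held | 0.34 | 29–61% |
| None through month 6, 1 unit at month 12 | 0.51 | 67–96% |

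In the first five rows the true 6-month difference is 1 unit and the direct contrast has about 90% power. In the last row the true 6-month difference is zero.

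**3. The quadratic clause.** As written it adds one quadratic term common to both arms. The arm difference stays linear and the table is unchanged. If the term was meant to differ by arm, the fitted 6-month difference in rows 2 to 5 is 0.94–1.00, close to the truth. But the linear time-by-intervention parameter is then the slope at baseline: 6 times it is 1.42–1.84, so testing that single parameter is still not a test of the 6-month difference.

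**4. If the model covered months 0–6 only.** The weights are −3, −1, 1 and 3, with sum of squares 20. A linear rise gives 6 × slope = 1.00 and power 93%. Full effect by month 2 gives 6 × 3/20 = 0.90 and power 85–86%. Little is lost.

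**5. If either test could claim success.** The 6-month contrast and the 0–12 slope are correlated 0.46 to 0.65, so type I error at a nominal 1% is 1.8–1.9%. For a 0–6 slope the correlation is 0.95 to 0.96 and the error is 1.3–1.4%.

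**The case against.** The strongest counter-case has four parts.

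- **There is a ranking of sorts.** The SAP links the primary hypotheses to the mixed model twice and never to the t-test. That is fair, and it means the inflated type I error needs a reading no section states. But if the mixed model is the decider, the deciding test is the one that matches neither the endpoint nor the power calculation.
- **The matching t-test is planned and would be reported.** A reader would see the 6-month difference beside the slope. This limits the harm in reporting, but the plan does not say which result prevails when they disagree.
- **The 0–12 window is inferred.** The plot that includes month 12 also serves to describe maintenance, and the use of all data is a statement about missingness. On a 0–6 window the loss is small. This stands as a condition on the size; it also shows that an unstated choice settles whether the test works.
- **The trajectories and variances are assumed.** They are, and the ranges are not bounds: the constraint on s² allows τ² up to 4/36 = 0.11, and at 0.06 or 0.10 power in the held case falls to 42% or 28%. The case with no effect until month 12 has no support in the documents and only illustrates direction. It may also be said that a linear form would not be used for a curved course, but the quadratic term as written leaves the arm difference linear.

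**Conclusion.** The concern holds. The mismatch follows from the text alone: endpoint, aim and sample size are at month 6, and the stated decision rule is a time-by-intervention parameter with no time point or window. Following that rule as written can give a wrong answer about the 6-month effect in either direction, so this must be fixed and is not just missing detail.

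The size is conditional. It is large if the model runs over 0–12 months with a linear arm difference and the effect levels off or wanes after month 6. It is small if the model stops at month 6, and there is no loss of power if divergence continues linearly to month 12. The planned 90% power applies to the month-6 contrast and carries over to the slope only under some of these conditions.

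**What to change.** Name one primary test: the between-arm contrast in DASH change at month 6. The preferred source is a mixed model with visit as a category (baseline, 2, 4, 6 and 12 months), arm-by-visit terms and the stratification factors, which keeps the planned likelihood handling of missing data. Making the existing 6-month t-test the sole primary would also resolve the mismatch.

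Then:

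- label the other analysis supportive;
- state the time window of any model;
- drop the plot-based choice of time form for the primary test;
- report the 12-month contrast as the secondary maintenance result;
- apply the same approach to systolic and diastolic pressure, and align the protocol's analysis section.

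The cost is SAP and protocol wording and a few more model parameters. Data, software and sample size do not change.
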